4.3.2. Patient-Reported Outcomes and Quality-of-Life Endpoints

PRO and Quality of life characteristics will be explored via the following endpoints:

- Median time to deterioration defined as the first occurrence of ≥ 10 -point decrease from baseline on the overall Functional Assessment of Cancer Therapy-Prostate (FACT-P¹) score.
- Change from baseline to each visit in the overall FACT-P score, as well as its subscales measuring physical and emotional well-being, prostate-cancer specific quality of life.
- Percentage of patients who filled out the survey and showed a 10-point improvement in FACT-P score.

4.3.3. Exploratory Pharmacodynamic Endpoints

- Change from baseline in serum cortisol and ACTH will be summarized by visit and arm.

5. Sample Size Calculation

The number of patients in the Dose-Determination Phase will depend on the number of cohorts assessed and the DLTs observed.

In Dose-Determination Phase Segment 1, an adequate number of DLT-evaluable patients will be enrolled to determine the RP2D for BID dosing. Expanded cohorts of 6 to 9 patients per dose level will be enrolled to better define the MTD/biologically active doses and for determination of the RP2D.

In Segment 2, approximately 20 patients will be enrolled (to achieve 16 DLT-evaluable patients) to determine the RP2D for QD dosing under fed conditions. Patients who discontinue treatment prior to completion of Cycle 3 and are not evaluable for DLTs may be replaced to include an adequate number of patients to assess the safety and tolerability of the regimen. If 2 to 4 patients are non-evaluable for DLTs, 4 additional patients will be enrolled. If 5 to 6 patients are non-evaluable for DLTs, 6 additional patients will be enrolled.

Approximately 40 patients will be enrolled in the Expansion Phase.

- Twenty patients in the Abi-Resistant Cohort will ensure at least 80% power for detecting a doubling of the background rate of 23.5% in the PSA responder, defined as $\geq 50\%$ improvement in the PSA level from baseline. This calculation assumes a 1-sided 0.1 significance level exact test of a single proportion against a fixed alternative. Under these assumptions, an absolute response rate of 40%, which represents a 59% improvement over the background rate, will support further evaluation of the regimen in the clinical program.
- Twenty patients in the ARant-Resistant Cohort will ensure at least 80% power for detecting an absolute improvement of 18% in the PSA responder rate over a rate of 8%, based upon the assumption that a response rate of 8% or less indicates no benefit. This calculation assumes a 1-sided 0.1 significance level exact test of a single proportion against a fixed alternative. Under these assumptions, an absolute response rate of 20%, which represents an improvement of 12% over the background rate, will support further evaluation in the clinical program

6. Analysis Populations

6.1. Intent-To-Treat Analysis Population

Intent-to-Treat Population (ITT): All patients who received at least 1 dose of the combination (exicorilant + enzalutamide) study treatment. The ITT Population will be used for efficacy analyses.

6.2. Safety Analysis Population

Safety Population: All patients who received at least 1 dose of exicorilant. All safety analyses, except evaluation of DLTs, will be based on the Safety Population.

6.3. DLT Analysis Population

DLT-Evaluable Population: The DLT-Evaluable Population will include all patients in the Dose-Determination Phase cohorts who receive at least 1 dose of exicorilant and fulfill at least 1 of the following:

- Complete at least the following durations of study treatment:
 - a. Segment 1: 28 days of continuous treatment with exicorilant
 - b. Segment 2: 3 cycles (≥ 84 days) of exicorilant + enzalutamide
 - c. Have received $\geq 75\%$ of exicorilant and enzalutamide doses during the DLT-evaluation period
- Experience a DLT within the DLT-evaluation period.

Patients who have received <75% of the study regimen due to reasons other than toxicity or who withdraw from the study prior to completion of the DLT-evaluation period for reasons other than toxicity will be considered non-evaluable for DLTs.

6.4. Pharmacokinetics Analysis Population

The PK-Evaluable Population (PK population) will be a subset of the Safety population and will include all patients who receive active study treatment and have measurable plasma concentration of study treatment at any time point. Prematurely discontinued patients and patients with missing sample concentrations will be included in PK analyses provided their PK parameters can be adequately characterized based upon the remaining data. All PK analyses will be based on the PK population.

7. General Analytical Considerations

The statistical principles applied in the design and planned analyses of this study are consistent with International Council for Harmonisation (ICH) E9 guidelines (ICH 1998) and Guidance for Industry Clinical Trial Endpoints for the Approval of Cancer Drugs and Biologics (2007).

All analyses will be completed using version 9.4 or later of the SAS Statistical Analysis System (SAS Institute, Inc, Cary, NC).

7.1. Data Sources

The study center staff will record completion and results of required study procedures in an electronic case report form (eCRF). Bioanalytical and laboratory data will be combined with the eCRF for analysis, after reconciled by [REDACTED]. CDISC SDTM domains will be prepared and used as the source data for the statistical summary and analysis.

7.2. Definitions

Study day: Study day will be calculated in reference to the date of the first dose of exicorilant. For assessments conducted on or after the date of the first dose of exicorilant, study day will be calculated as (assessment date - date of first dose of study drug + 1). For assessments conducted before the date of the first dose of exicorilant, study day is calculated as (assessment date - date of first dose of study drug). There is no study day 0.

Treatment-emergent period: The treatment-emergent period is defined as the period of time from the date and time of the first dose of exicorilant through 30 days after the last dose of

study drug (exicorilant or enzalutamide whichever is later). The treatment-emergent period will be used in the summaries of treatment-emergent adverse events (TEAEs).

Baseline and postbaseline value: Unless otherwise specified, a baseline value will be defined as the most recent value on or before the first dose of exicorilant including PRO, QoL and baseline characteristics. In addition, pretreatment Cycle 1 Day 1 values could serve as baseline. A postbaseline value is defined as an assessment obtained after the first dose of exicorilant.

Baseline and postbaseline value for safety analyses: Unless otherwise specified, a baseline value for safety analyses is defined as the last value on or before the date/time of first dose of exicorilant for laboratory tests, vital sign assessments, and ECG data. A postbaseline value for safety analyses is defined as a measurement taken after the date/time of first dose of exicorilant. If multiple toxicity grades are present for the same date, the worst toxicity grade will be used in the summaries of toxicity grade by laboratory tests. For triplicate measurements of ECG, worst results will be used in the summaries presented by visit. For all other safety parameters, if multiple measurements are present for the same date, latest available value will be considered for summaries.

Last dose date: Date of last dose of exicorilant or enzalutamide (whichever is last) from the end of treatment – exicorilant and enzalutamide eCRFs.

7.3. Reporting Conventions

Unless otherwise specified, the following conventions will be applied to all analyses:

- Mean and median values will be formatted to 1 more decimal place than the measured value. Standard deviation values will be formatted to 2 more decimal places than the measured value; minimum and maximum values will be presented to the same number of decimal places as the measured value.
- Percentages will be rounded to 1 decimal place. Number and percentage values will be presented as xx (xx.x%).
- Listings will be sorted for presentation in order of patient identifier and date of procedure or event.
- Analysis and summary tables will have the analysis population sample size (ie, number of patients).
- Laboratory data will be reported using standard international (SI) units; as local laboratories are used for this study, conversion factors from conventional units will be listed in the clinical study report. For example: 1 inch = 2.54 cm.
- Time-to-event or duration of event endpoints will be based on the actual date the radiographic scan was obtained rather than the associated visit date.
- For by-visit observed data analyses, percentages will be calculated based on the number of patients with non-missing data as the denominator unless otherwise specified.

- For time-to-event right-censored data, the summary statistics and descriptions will include Kaplan-Meier plots and/or life tables.
- For other continuous endpoints, the summary statistics will include mean, standard deviation, median, and range (minimum and maximum).
- For categorical endpoints, the summary statistics will include frequency counts and percentages.
- Confidence intervals (CIs), when presented, will generally be constructed at the 95% level. For binomial variables, Clopper-Pearson method methods will be employed unless otherwise specified.
- Medical history and adverse events will be coded using the Medical Dictionary for Regulatory Activities (MedDRA v 20.1 or later. Adverse event severity will be evaluated using the National Cancer Institute Common Terminology Criteria for Adverse Events (CTCAE v.5.0).
- Prior therapies and concomitant medications will be coded using the World Health Organization (WHO) Drug Dictionary and summarized by Anatomical Therapeutic Chemical (ATC) therapeutic subgroup and preferred drug names.

PK Reporting Conventions:

PK parameters will be summarized using n (for available data), mean, standard deviation (SD), coefficient of variation percent (CV%), median, minimum, and maximum values, geometric mean, and geometric CV%.

Derived PK parameters will be rounded for reporting purposes in the by-patient listings. For calculation of descriptive statistics and statistical analysis, rounded values as presented in the data listings will be used. For most derived PK parameters, 3 significant digits will be used as the standard rounding procedure, with the following exceptions:

- Parameters directly derived from source data (e.g. C_{max}) will be reported and analyzed with the same precision as the source data.
- Parameters derived from actual elapsed sample collection times (e.g. t_{max}) will be reported to 3 decimal places.

Reporting of minimum, median, and maximum will follow the rounding convention of the individual PK variables. Means, any associated CI, and SD will be presented to one digit more precision than the source data. Coefficients of variation will always be reported to 1 decimal place.

Conventions for Dates:

Conventions for calculations with dates are as follows:

- Dates will be stored as numeric variables in the statistical analysis software (SAS) analysis files and reported in DDMMYYYY format (ie, the Date9. datetime format in SAS).

- Dates recorded in comment fields will not be imputed or reported in any specific format.
- Intervals that are presented in weeks will be transformed from days to weeks by using the following conversion formula, and rounding to 1 decimal place: $WEEKS = DAYS / 7$
- Intervals that are presented in months will be transformed from days to months by using the following conversion formula, and rounding to 1 decimal place: $MONTHS = DAYS / 30.4375$

7.4. Handling of Missing Data

Missing data will not be imputed unless otherwise specified. Missing dates or partially missing dates will be imputed conservatively for adverse events and prior/concomitant medications/procedures.

For safety analyses, incomplete date of last dose of study drug and incomplete start date of a new antitumor treatment that are missing the day of the month, the 15th of the month will be used to impute the missing data. When imputing partial last dose dates, the last assessment date and death date will be taken into consideration. This imputation rule will be used to determine the treatment-emergent period.

Adverse Events

The imputation rule for the safety analyses will be used to address the issues with partial dates. The imputed dates will be used to determine the treatment-emergent period. For adverse events with a partial date, available date parts (year, month, and day) of the partial date will be compared with the corresponding date components of the start date and end date of the treatment-emergent period to determine if the event is treatment emergent. When in doubt, the adverse event will be considered treatment emergent by default. The following rules will be applied to impute partial dates for adverse events:

If start date of an adverse event is partially missing, impute as follows:

- If both month and day are missing and year = year of treatment start date, then set to treatment start date
- If both month and day are missing and year \neq year of treatment start date, then set to January 01
- If day is missing and month and year = month and year of treatment start date, then set to treatment start date
- If day is missing and month and year \neq month and year of treatment start date, then set to first of the month
- If only year is missing or start date is completely missing, set to treatment start date as long as adverse event end date is not before treatment start date

If end date of an adverse event is partially missing, impute as follows:

- If both month and day are missing, then set to December 31
- If only day is missing, then set to last day of the month
- If only year is missing or end date is completely missing, do not impute

Concomitant Medications

When the start date or end date of a medication is partially missing, the date will be imputed to determine whether the medication is prior or concomitant (or both). The following rules will be applied to impute partial dates for medications:

If start date of a medication is partially missing, impute as follows:

- If both month and day are missing, then set to January 01
- If only day is missing, then set to the first of the month

If end date of a medication is partially missing, impute as follows:

- If both month and day are missing, then set to December 31
- If only day is missing, then set to last day of the month

If only year is missing or start date or end date of a medication is completely missing, do not impute.

Primary Cancer Diagnosis

If the diagnosis date of primary cancer is partially missing, the following rules will be applied to impute partial dates:

- If both month and day are missing and year = year of treatment start date, then set to treatment start date.
- If both month and day are missing and year \neq year of treatment start date, then set to December 31.
- If day is missing and month and year = month and year of treatment start date, then set to treatment start date.
- If day is missing and month and year \neq month and year of treatment start date, then set to the last day of the month

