Bone disease progression: For the Response-Evaluable population, bone disease progression, defined as time from first dose of study treatment (exicorilant and/or enzalutamide) to first confirmed appearance of at least 2 new bone metastatic lesions, will be estimated via the Kaplan-Meier method. Cases of equivocal progression will be confirmed by a repeat scan 8 weeks later. Patients who are alive and progression-free will be censored at their end of study visit. Median time to progression and associated 95% CIs will be summarized, overall and by treatment group. Kaplan-Meier graph of the probability of the event will also be plotted by treatment group.

Overall survival (OS): Overall survival will be calculated as the time from the first dose of study treatment (exicorilant and/or enzalutamide) to the date of death from any cause. Deaths that occur on or before the data cutoff date will be considered an event. If a patient has not died before the analysis cutoff date, OS will be censored at the date of last contact on or before the data cutoff date. The last contact date will be derived as follows:

Source Data Conditions	Source Data Conditions
Date of randomization	No condition
Last contact date/last date patient known to be alive from Long-Term Follow-Up eCRF	Use if patient status is reported to be alive Do not use if patient status is reported unknown
End of study	Not lost to follow up
Start/end dates of postbaseline antineoplastic therapy	Nonmissing medication/procedure term
Start/end dates from drug administration record	Nonmissing dose. Doses of 0 are allowed.
End of treatment date from the End of Treatment eCRF	No condition
Investigator overall tumor response assessment date	Evaluation is marked as done.
Laboratory/PK collection dates	Sample collection marked as done.
Vital signs date	At least 1 nonmissing parameter value
ECOG performance status date	Nonmissing ECOG performance status
Start/end dates of adverse events	Nonmissing verbatim term
Physical examination	Evaluation is marked as done.
ECG	Evaluation is marked as done.

The OS in months is defined as follows:

$$\text{OS (months)} = (\text{earliest date of death or censoring} - \text{date of first study treatment} + 1) / 30.4375$$

Median, 25th and 75th percentiles of OS, in months, with 95% CIs will be summarized and plotted graphically by treatment arm and overall using the Kaplan-Meier method.

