10.1. Adverse Events

Per protocol, adverse events will be collected from the time of signing the ICF until 30 days after the last dose of exicorilant or enzalutamide. Illnesses present before the patient signs the ICF will be considered pre-existing conditions and documented on the medical history eCRF.

Pre-existing conditions that worsen during the study will be entered on the AE eCRF. Adverse events that occur after the first dose of exicorilant through 30 days after administration of the final dose of study treatment will be considered treatment-emergent adverse events (TEAEs). Adverse events reported more than 30 days after the last dose of study treatment will be considered post-treatment AEs.

Incidence of TEAEs will be listed and summarized using the current version of Medical Dictionary for Regulatory Activities (MedDRA v20.1 or later) by system organ class and preferred term. A hierarchical listing will display the MedDRA system organ classes represented in the data, and within each system organ class, the listing will display each unique preferred term ordered alphabetically. At each level of summation of system organ class and preferred term, patients reporting more than one AE will only be counted once. Similarly, multiple incidences of the same AE for each patient will be reported only once at the maximum severity. If relationship to study drug is missing, the adverse event will be counted as related. Adverse event listings will show missing relationship as missing.

All AEs (whether TEAEs or not) will be listed in a listing by treatment group and individual patient, including dates of onset and resolution, whether ongoing, or serious, CTCAE toxicity grade, action taken and relationship to study drug. Serious TEAEs and TEAEs that lead to withdrawal from exicorilant or enzalutamide will be listed separately.

Summary tables will be provided for:

- Overall summary of TEAEs.
- TEAEs occurring 10% or higher in the Safety population by preferred term and CTCAE grade.
- All TEAEs.
- Grade 3 or greater TEAEs.
- TEAEs related to exicorilant.
- TEAEs related to enzalutamide.
- Grade 3 or greater TEAEs related to exicorilant.
- Grade 3 or greater TEAEs related to enzalutamide.
- Grade 3 or greater TEAEs related to exicorilant and enzalutamide.
- Serious TEAEs
- TEAEs leading to withdrawal of exicorilant.
- TEAEs leading to withdrawal of enzalutamide.
- TEAEs requiring dose interruption or reduction of exicorilant.

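### Two of the five AE start-date imputation rules in SAP 7.4 lack the end-date check that the fifth has, so an AE that ended before exicorilant can be counted as treatment-emergent

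*SAP*

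**What the plan says.** SAP 7.4 (Adverse Events) gives five rules for a partial or missing AE start date. Two assign the treatment start date because the known parts match it: "If both month and day are missing and year = year of treatment start date, then set to treatment start date" and "If day is missing and month and year = month and year of treatment start date, then set to treatment start date". Two others, for a known year or month that does not match, assign 1 January or the first of the month. The fifth, for a missing year or a wholly missing date, also assigns the treatment start date, but on a condition: "set to treatment start date as long as adverse event end date is not before treatment start date".

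The same section compares the available parts of the partial date with the treatment-emergent period and adds a tie-break: "When in doubt, the adverse event will be considered treatment emergent by default". It does not define treatment start date.

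SAP 7.2 starts the treatment-emergent period at the first dose of exicorilant, and SAP 13 records this as a change from the protocol, which used first study treatment. SAP 10.1 states that "adverse events will be collected from the time of signing the ICF". The AE data therefore include events from screening (up to 28 days before first study treatment) and from the planned 28-day enzalutamide lead-in of Segment 1. SAP 10.1 also plans a separate table of AEs occurring only during that lead-in.

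**The concern.** Three of the five rules can place a start on the day of first treatment, but only one of them asks whether the event had already ended. Under the other two, a resolved event with an incomplete start date is given an impossible record, with onset after resolution, and that onset falls inside the treatment-emergent period.

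At stake is attribution. An event that ended during screening, or on enzalutamide alone, would be reported as emerging on exicorilant. In Segment 1 it would also leave the lead-in-only table, which exists to keep such events apart. This undoes what the change in SAP 13 set out to achieve. Because the dose groups are very small, one misplaced event visibly changes a percentage.

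**Working it through.** The plan states no figure on this point, so there is none to reproduce. The check applies the rules literally, taking treatment start as the first exicorilant dose.

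**Step 1. Can each start-date rule pass the AE's own end?**

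| Known part of start date | Imputed start | End-date check? | Can fall after a known AE end? |
|---|---|---|---|
| Year only, same year as treatment start | Treatment start | No | Yes |
| Year only, other year | 1 January | No | No, earliest possible date |
| Month and year, same as treatment start | Treatment start | No | Yes |
| Month and year, other | First of month | No | No, earliest possible date |
| Year missing or nothing known | Treatment start | Yes | No |

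**Step 2. Illustrative dates.** First exicorilant is 25 September 2020 and the AE ended on 10 September 2020.

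- Start known only as September 2020: the imputed start is 25 September. End minus start is 10 − 25 = −15 days, and the AE counts as a TEAE.
- Start known only as 2020: same result.
- With the end date as an upper limit on the imputed start: the start is 10 September, the duration is 0 days, and the AE is not a TEAE.
- Start known only as August 2020: the imputed start is 1 August, 40 days before the end, and the AE is not a TEAE. This rule behaves correctly.

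**Step 3. How often the rules misfire, given a partial start date.** The grid takes every exicorilant start date in 2020 and 2021 (366 + 365 = 731 days). Each is combined with every AE that began 1 to W days earlier and ended before exicorilant. An AE that began k days earlier has k possible end days, so each start date yields W(W+1)/2 combinations:

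- W = 28 (one 28-day period before exicorilant): 28 × 29 / 2 = 406, and 406 × 731 = 296,786.
- W = 56 (28 days of screening plus the 28-day lead-in): 56 × 57 / 2 = 1,596, and 1,596 × 731 = 1,166,676.

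| Missing part of start date | W = 28: becomes a TEAE | W = 56: becomes a TEAE |
|---|---|---|
| Day | 37.6% | 9.7% |
| Month and day | 94.8% | 89.7% |

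In every affected combination the imputed start is later than the true end. The largest forward shift of the start is 28 days with W = 28. With W = 56 it is 30 days (day missing) or 56 days (month and day missing). The day-missing share falls in the longer window because most added combinations begin in an earlier calendar month, where the safe rule applies. These are shares of date combinations, not estimates of real frequency.

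**Step 4. Who is exposed.** Screening AEs are exposed in every phase. Lead-in AEs are exposed only where there was an enzalutamide lead-in. Protocol 1.3.2.1 reports 2 patients given exicorilant in Cohort 1 and 3 in Cohort 2, so 2 + 3 = 5. SAP 8.8 shows Cohort 3 without a lead-in, and SAP 2.1 plans none for Segment 2. One patient is 1/2 = 50% of Cohort 1 or 1/3 = 33% of Cohort 2.

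**The case against.** **Imputation is meant to be conservative, and doubt resolves towards treatment-emergent.** That is a sound default for an event whose timing is unclear. It does not cover this case, because a known end before first exicorilant leaves no doubt. The date-part comparison in 7.4 does not catch the error either, since it uses only the parts of the partial date.

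**Treatment start date is undefined, and Protocol section 5 defines study treatment as CORT125281 and/or enzalutamide.** This objection has force. If the term means the first lead-in enzalutamide dose, a re-dated Segment 1 lead-in AE falls before exicorilant and does not become a TEAE by this rule. That reading brings its own error: an AE that truly began after exicorilant in the same month or year could be back-dated into the lead-in. Either way, the term needs a definition.

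**Other safeguards exist.** A footnote to Protocol Table 12 says screening-period AEs are not treatment-emergent, all AEs are listed with onset and resolution dates, and DLTs are determined by investigator review. The primary endpoint is therefore not affected, and a careful reader of the listings could spot an onset after resolution. The TEAE tables, however, would be programmed from the SAP rules, and those rules contradict the footnote.

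**Few patients had an enzalutamide lead-in.** True: about five in the Safety Population, as of the protocol's clinical update. A reader might take the share of lead-in days in the same calendar month as the first dose and infer that this share of lead-in AEs is misclassified. That would be wrong, because it includes AEs still ongoing at first exicorilant. The defect concerns only those that had ended.

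**Conclusion.** The defect holds for the same-month and same-year start-date rules. Read with treatment start as first exicorilant, they date an AE with a known earlier end after that end and count it as a TEAE. Given a partial start date, the shares are those in Step 3. The number of AEs actually affected cannot be estimated, because the documents do not say how often start dates are partial. The consequence is confined to the TEAE summaries and the lead-in-only table.

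Two stronger readings are not supported.

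- A reader might infer that the AE date rules have no bounds at all. One start rule is guarded, two cannot overshoot, and for end dates 7.4 says "If only year is missing or end date is completely missing, do not impute".
- A reader might combine the year-only end-date rule ("If both month and day are missing, then set to December 31") with the OS last-contact table in SAP 9.1, which lists "Start/end dates of adverse events", and infer that imputed dates lengthen OS censoring times and bias the survival curve upward. The documents do not say so. SAP 7.4 opens by ruling out imputation unless specified, and gives determining treatment emergence as the use of imputed AE dates. SAP 9.1 limits last contact to the data cutoff, and recorded deaths by cutoff are events. What remains is that 9.1 does not expressly exclude imputed dates, which calls for a clarification and does not show a bias.

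**What to change.** In SAP 7.4 (Adverse Events):

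1. State that treatment start date means the date of the first exicorilant dose.
2. Apply the end-date check of the fifth start-date rule to the same-month and same-year rules. An imputed start is then never later than a known AE end, and an AE that ended before first exicorilant is not treatment-emergent.

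As a clarification in SAP 9.1, add that the OS last-contact date is derived from complete, non-imputed dates only.

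The cost is about three sentences of SAP wording and the matching change in the AE date derivation. No new data are needed, and sample size, power and significance level do not change.
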